12.4.2 Baseline-adjusted Pharmacodynamic Data

Individual serum concentrations of PD markers, calcium (uncorrected and corrected for albumin), phosphate and calcium-phosphate product will be baseline-adjusted at each time point. Albumin-corrected calcium will be used to calculate the calcium-phosphate product. Baseline adjustment is subject- and dose-specific. For each subject, baseline is defined for each dosing period as follows: the baseline for Day 1 dosing is defined as the predose concentration on Day 1; the baseline for Day 4 dosing is defined as the predose concentration on Day 4; the baseline for Day 7 dosing is defined as the predose concentration on Day 7. Baseline-adjusted concentrations of PD markers are to be calculated by subtracting the appropriate baseline values from the original concentrations at each time point. If the baseline-adjusted concentration gives a negative value then the baseline-adjusted concentration should be set to zero.

Individual baseline-adjusted concentrations of serum total calcium, albumin-corrected calcium, phosphate and calcium-phosphate product will be listed and summarized with descriptive statistics (number, arithmetic mean, SD, CV%, median, minimum, maximum,) by ethnic group, dose and time point.

Figures of individual baseline-adjusted concentration-time profiles and mean (\pm SD) will be generated on linear scale for serum total calcium, albumin-corrected calcium, phosphate and calcium-phosphate product by ethnic group and dose. The mean plots will be created for the baseline-adjusted concentrations of the above four PD markers by overlaying all ethnic groups and doses on the same figure.

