1.2.2 Clinical Information

Few studies of PTH use have been performed in the setting of hypoparathyroidism. Study CL1-11-040 (REPLACE) was a double-blind, placebo controlled study of once daily (QD) administration of 50 μ g, 75 μ g, or 100 μ g of rhPTH(1-84) which resulted in 54.8% of the rhPTH(1-84) subjects meeting a 3-tiered primary endpoint vs 2.5% of the placebo subjects ($p<0.001$). Long-term, open-label studies have supported these findings with subjects maintaining the physiologic benefit derived from rhPTH(1-84) treatment. One study, PAR-C10-008 (RACE), is ongoing with subjects receiving treatment for more than 5 years.

In clinical trials, rhPTH(1-84) significantly reduced the calcium-phosphate product. In these studies hypercalciuria was defined as an excretion of calcium in the urine greater than 300mg per 24 hours. Data from the REPLACE Study and the long-term open label study, RACE, show that rhPTH(1-84) has a calcium-sparing effect, consistent with the reduction of calcium excretion seen in a previous PK/PD study (C09-002) of single dose administration of rhPTH(1-84) in patients with hypoparathyroidism in comparison with calcitriol administration.

The Phase 3 clinical study, REPLACE, was the largest, randomized, placebo controlled clinical study conducted in hypoparathyroidism population and was the pivotal study demonstrating that rhPTH(1-84) is effective in maintaining serum calcium levels and enabling significant decreases in active vitamin D and oral calcium doses. REPLACE also established the rhPTH(1-84) dose and dose titration and evaluated the physiologic effects of PTH replacement on serum calcium, serum phosphate, urinary calcium excretion, and bone turnover markers. Eighty-four subjects were evaluated in the active treatment group and 40 subjects received placebo. Subjects received 50 μ g, 75 μ g, or 100 μ g SC in the thigh once daily for 6 months. The study met the primary efficacy triple endpoint, with a statistically higher responder rate (54.8%) versus placebo (2.5%). To meet the primary endpoint a subject had to fulfill all 3 conditions as follows: a 50% or greater reduction in oral calcium requirement, a 50% or greater reduction in active vitamin D therapy and an albumin corrected serum calcium (ACSC) concentration that was maintained within a range of 7.5 to 10.6 mg/dL.

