2. STUDY OBJECTIVES AND PURPOSE

2.1 Rationale for the Study

Recombinant human PTH (rhPTH[1-84]) is approved for use in the United States (US) as an adjunct to calcium and vitamin D to control hypocalcemia in patients with hypoparathyroidism. As a once-daily SC injection for hypoparathyroidism, it has been shown to provide a 24-hour sustained increase in serum calcium. Administration of rhPTH(1-84) resulted in dose-related increases in total serum calcium levels, with maximum mean increases (approximately 0.125 to 0.175 mmol/L) observed 12 hours after dosing. Serum calcium levels did not return to baseline levels by 24 hours. This sustained increase may explain the reduction in the observed daily amounts of calcium and active vitamin D that were taken in the placebo-controlled trial.

Shire intends to develop rhPTH(1-84) for use in Japan. The Japanese regulatory agencies, Pharmaceuticals Medical Devices Agency (PMDA) and the Ministry of Health, Labor and Welfare (MHLW), require evidence that current data in non-Japanese subjects can be extrapolated to the Japanese population, since Japanese patients may require different doses of medication of some drug classes.

To satisfy the PMDA and MHLW requirements, sponsors will provide data to support doses for a later study in Japanese subjects. The present study to compare PK and PD profiles and safety and tolerability in Japanese and Non-Hispanic, Caucasian healthy volunteer subjects is designed for this reason. In addition, this study will also assess the PK dose-proportionality of rhPTH(1-84) using three, randomized, single, SC doses of 25 μ g, 50 μ g, and 100 μ g in healthy volunteers of Japanese descent.

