9.8.3 Statistical Analysis of Pharmacodynamic Values

Individual values (original and baseline-adjusted) and PD parameters (original and baseline-adjusted) of serum total calcium, albumin-corrected calcium, phosphate and the calcium-phosphate (albumin-corrected calcium) product will be summarized with descriptive statistics (number, arithmetic mean, SD, CV%, median, minimum, maximum, geometric mean, and geometric CV%). Figures of individual and mean ($\pm SD$) concentration-time profiles of the original and baseline-adjusted PD markers, serum calcium (total and corrected for serum albumin) and phosphate, will be generated. Mean plots will be overlaid for the Japanese cohort and the Non-Japanese cohort. Box-Whisker plots for selected PD parameters will be prepared with the Japanese cohort and Non-Japanese cohort side by side.

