^k There must be a minimum washout period of 72 hours (maximum 73 hours) from dose to dose for the volunteers of Japanese descent.

^l SAEs will be followed to resolution

Table 2 Detailed Schedule of Assessments (non-Hispanic, Caucasian Subjects)

Study Day	Day 1																	Day 2	
	Pre Dose 1	Pre Dose 2	0	10m	20m	30m	45m	1h	1.25h	1.5h	2h	2.5h	3h	4h	6h	8h	12h	16h	
Physical examination ^a																			X
Vital signs (BP, temperature and pulse) ^{a,b}		X ^e						X					X	X					X
TriPLICATE Electrocardiogram (12-lead) ^{a,c}		X ^e																	X
Biochemistry, hematology, and urinalysis ^a		X ^e																	X
Serum β-hCG Pregnancy test (females only) ^a																			X
Investigational drug administration			X																
Pharmacodynamic blood sampling ^d		X ^e												X	X	X			X
Anti-PTH antibody sampling		X ^e																	
Pharmacokinetic blood sampling	X ^f	X ^e		X	X	X	X	X	X	X	X	X	X	X	X	X	X	X	

BP=blood pressure; ECG=electrocardiogram; PK=pharmacokinetic, PTH=parathyroid hormone

^a In the event a subject is prematurely discontinued from the study or withdraws, every attempt should be made to complete these assessments.^b Vital signs will be obtained while subject is supine at times noted. Temperature only to be obtained at screening and at predose on Day 1.^c Electrocardiograms will be performed in triplicate at each timepoint.^d Pharmacodynamic blood sampling assessments will include serum calcium and phosphate and must be drawn before PK samples at the same timepoint.^e These assessments should be performed within 30 minutes prior to dose administration. The urine collection may be the first void of the day [providing that it is predose] but may be outside the 30 minute window if necessary.^f These assessments should be performed within 90 (±30) minutes prior to dose administration.

Table 3 Detailed Schedule of Assessments (Subjects of Japanese Descent)

Study Day	Days 1, 4 and 7																		Days 2, 5 and 8
	Pre-dose 1	Pre-dose 2	0	10m	20m	30m	45m	1h	1.25h	1.5h	2h	2.5h	3h	4h	6h	8h	12h	16h	
Hour (relative to dosing time)																			24h
Physical examination ^a																			X ^h
Vital signs (BP, temperature and pulse) ^{a,b}		X ^e						X					X		X				X
TriPLICATE Electrocardiogram (12-lead) ^{a,c}		X ^e																	X
Biochemistry, hematology, and urinalysis ^a		X ^e																	X
Serum β-hCG Pregnancy test (females only) ^a																			X ^h
Investigational drug administration			X																

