2.6 Multiplicity Adjustments for Type I Error Control

Not applicable, as the statistical analyses are for exploratory rather than confirmatory purposes.

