3.2 Secondary Objectives

- To assess the dose proportionality of the selected PK parameters of rhPTH(1-84) in healthy adult volunteer subjects of Japanese descent when exposed to single SC doses of rhPTH(1-84) at 25 μ g, 50 μ g, and 100 μ g.
- To compare the PD profile (serum calcium and phosphate concentration levels vs time) of a 100 μ g SC injection of rhPTH(1-84) in healthy adult volunteer subjects of Japanese descent and matched, non- Hispanic, healthy, adult Caucasian, subjects.
- To assess the PD profile (serum calcium and phosphate concentration levels vs time) of a 25 μ g and 50 μ g SC injection of rhPTH(1-84) in healthy adult volunteer subjects of Japanese descent.
- To assess the safety and tolerability of single SC doses of 25 μ g, 50 μ g, and 100 μ g of rhPTH(1-84) in healthy adult volunteer subjects of Japanese descent.
- To evaluate the safety and tolerability of a 100 μ g SC injection of rhPTH(1-84) in matched, non-Hispanic, healthy, adult volunteer Caucasian subjects.

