11. SAFETY ANALYSES

The safety analysis will be performed using the Safety Analysis Set. Safety variables include AEs and TEAEs, clinical laboratory variables, vital signs, and ECG variables. For clinical laboratory and vital sign variables, the last value collected before the dose administration will be used as baseline for all analyses of that safety variable in the respective dose interval. Thus there will be a different baseline for each dose for the Japanese subjects.

Follow-up visits will be summarized under the 100 μ g dose, regardless of which sequence the subject was randomized to, or which doses they had received.

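### The zero floor in SAP 12.4.2 stops the baseline-adjusted phosphate and calcium-phosphate product outputs from showing a fall

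*SAP*

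**What the plan says.** SAP 12.4.2 defines the baseline-adjusted PD value as the post-dose concentration minus the predose concentration of the same dosing day, so a fall is a negative number. It covers total calcium, albumin-corrected calcium, phosphate and the calcium-phosphate product. It then adds, with no exception by marker: "If the baseline-adjusted concentration gives a negative value then the baseline-adjusted concentration should be set to zero".

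The floored values feed the by-time summaries and the individual and mean plots (12.4.2), AUClast, Emax and TEmax (12.4.3), and the parameter summaries and 100 µg box plots (12.4.4). For phosphate and the product these include Tables 2.2.7, 2.2.8, 2.2.15 and 2.2.16.

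Protocol 9.8.3 plans to summarise "Individual values (original and baseline-adjusted) and PD parameters (original and baseline-adjusted) of serum total calcium" and of the other markers. Neither 9.8.2 nor 9.8.3 mentions a floor, and SAP section 17 does not list one as a change. One secondary objective in SAP 3.2 is "To compare the PD profile (serum calcium and phosphate concentration levels vs time) of a" 100 µg injection in Japanese and Caucasian subjects. Another covers the same markers at 25 and 50 µg in Japanese subjects.

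On direction, Protocol 1.2.2 states: "In clinical trials, rhPTH(1-84) significantly reduced the calcium-phosphate product". Protocol 2.1 describes dose-related rises in calcium, "with maximum mean increases (approximately 0.125 to 0.175 mmol/L) observed 12 hours after dosing".

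**The concern.** SAP 12.3.2 has the same floor for PTH. There it makes sense, because the target is a positive increment of administered hormone above an endogenous background. A change from baseline in phosphate or in the product has no such lower limit. If calcium rises and the product falls, phosphate must have fallen.

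Under the rule every fall, small or large, becomes zero and only upward deviations survive. This has four consequences:

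- Group means are zero or positive whatever the true fall, and a group with a stronger fall tends to report a smaller mean.
- If more than half of a group falls at a time point, the reported median there is exactly zero.
- A subject with no value above baseline gets AUC = 0 and Emax = 0, and TEmax is arbitrary because all values tie.
- A single zero makes the geometric mean and geometric CV% planned in 12.4.4 impossible to compute on all subjects.

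SAP 12.4.3 also gives no direction for the maximum effect, so nothing there restores the lost information. At stake is the baseline-adjusted half of the phosphate evidence for two secondary objectives.

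**Working it through.** The documents give no expected phosphate change, no SD and no figure to reproduce on this point. The rule itself can be checked exactly. Its numerical effect needs assumptions, marked below.

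**Inputs from the documents.** Reported value = max(0, post-dose − predose). PD samples are taken predose and at 4, 8, 12 and 24 h (SAP 12.4.1). There are 12 subjects per group (SAP 2.5). Peak mean calcium rises are 0.125 to 0.175 mmol/L (Protocol 2.1).

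**Assumed.** Changes are normal with SD 0.05 to 0.15 mmol/L for phosphate and 0.04 to 0.08 for calcium. The phosphate falls are as stated in each step.

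**Formula.** For a change X with mean μ and SD σ, the expected floored value is E[max(X,0)] = μ·Φ(μ/σ) + σ·φ(μ/σ).

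**1. One time point, two groups with mean falls of 0.10 and 0.20 mmol/L (true contrast 0.10).**

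| SD | Floored mean, fall 0.10 | Floored mean, fall 0.20 | Floored contrast | Contrast lost |
|---|---|---|---|---|
| 0.05 | +0.0004 | +0.0000 | 0.0004 | over 99% |
| 0.10 | +0.0083 | +0.0008 | 0.0075 | 93% |
| 0.15 | +0.0227 | +0.0064 | 0.0163 | 84% |

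Both means are positive, and the group with the larger fall has the smaller one.

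**2. AUC over 0–24 h (linear trapezoid).** The weights at 4, 8, 12 and 24 h are 4, 4, 8 and 6 h. Assumed mean changes at 100 µg are −0.20, −0.15, −0.10 and −0.02 mmol/L, scaled in proportion to dose, with SD 0.10.

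- True AUC at 100 µg: 4(−0.20) + 4(−0.15) + 8(−0.10) + 6(−0.02) = −2.32 mmol·h/L. At 50 and 25 µg it is −1.16 and −0.58.
- Expected floored AUC at 100 µg: 0.003 + 0.012 + 0.067 + 0.184 = +0.266. At 50 and 25 µg it is +0.455 and +0.629, and with no drug effect +0.878. The dose order is inverted.
- The 24 h point supplies 0.184/0.266 = 69% of the 100 µg value. That is almost all noise, since the assumed effect there is only −0.02.
- At SD 0.05 and 0.15 the 100 µg value is +0.073 and +0.559.

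**3. Share of subjects with AUC exactly zero at 100 µg.** With independent errors this is the product of Φ(−μ/σ) over the four times: 0.444 at SD 0.10, 0.640 at 0.05 and 0.316 at 0.15. With errors correlated 0.5 and SD 0.10, simulation gives 0.525. The median subject AUC at SD 0.10 is about 0.065 with independent errors and 0 with correlated errors. With 12 subjects, the chance of at least one zero is 1 − (1 − 0.444)^12 = 0.999.

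**4. How often two groups of 12 reverse.** In 30,000 simulated trials, a group with twice the 100 µg effect reports the smaller mean floored AUC in 82% (independent errors) and 78% (correlation 0.5) at SD 0.10. Over SD 0.05 to 0.15 the range is 77–85%. Reversal is a tendency, not a rule.

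**5. Calcium.** Bias = E[max(X,0)] − μ. At the protocol's peak rises it is at most 0.002 mmol/L. At assumed rises of 0.03 to 0.06 it is 0.011 to 0.019 with SD 0.08 (17–64% of the rise) and 0.001 to 0.005 with SD 0.04 (2–17%).

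**The case against.** The best reply is that the floor affects a second, descriptive output set while the main one is intact. SAP 2.6 reads: "Not applicable, as the statistical analyses are for exploratory rather than confirmatory purposes". PD has no test, confidence interval or decision rule. The objective is worded as levels over time, and the unadjusted tables, overlaid plots, AUClast and box plots are not floored. Tables 2.2.3 and 2.2.4 are by group, dose and time point, and predose is a sampling time. With complete pairs, a reader could therefore subtract means and recover the signed mean change, and Listing 5.7 holds the individual values. SAP 11 and 11.2 also give signed laboratory change for phosphorus and calcium, where "the last value collected before the dose administration will be used as baseline" separately for each dose.

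These points stand and they limit the harm. They do not repair the rule. The safety panel ("Biochemistry, hematology, and urinalysis") is drawn only predose and at 24 h (SAP Tables 2 and 3). No planned table reports signed phosphate or product change at 4, 8 or 12 h, or its within-subject spread, and differences of unadjusted means do not supply that spread.

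Two further objections are fair. The reported fall concerns the product in hypoparathyroidism trials, so its direction and size after single doses in healthy subjects are an inference. Also, the SAP asks for AUC to the last measurable concentration and does not say whether a trailing floored zero counts as measurable. If it does not, the independent-error expectations at SD 0.10 become about 0.23, 0.38 and 0.52 at 100, 50 and 25 µg and 0.73 with no effect, and reversal drops to about 76%. The direction of the distortion is unchanged.

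**Conclusion.** The concern holds, with high confidence, and should be fixed. That the baseline-adjusted PD outputs cannot show a fall follows from the rule alone and needs no assumption. The size of the distortion is conditional on assumed phosphate falls, SDs and time course. Over the SDs tried for the single-time comparison, 84% to over 99% of a true 0.10 mmol/L contrast disappears. In the assumed dose-scaled profile the dose order of expected AUC inverts. Calcium is hardly affected at the rises the protocol quotes, so the practical problem lies with phosphate and the product. The consequence is misleading descriptive tables and plots for part of two secondary objectives. The primary PK comparison is not touched.

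**What to change.** - **SAP 12.4.2:** delete the zero-floor sentence and keep signed changes from baseline for all four markers.
- **SAP 12.2:** state that the BLQ rules apply to measured PD concentrations and not to signed changes. The section now names baseline-adjusted PD data as well.
- **SAP 12.4.3:** report baseline-adjusted AUC as signed net area to the last sample. Report both the maximum increase and the maximum decrease, each with its time, so that no undocumented direction is fixed in advance.
- **SAP 12.4.4:** summarise baseline-adjusted PD parameters with arithmetic mean, SD, median and range. Geometric statistics are undefined for zeros under the floor and for negative values without it.
- **SAP section 17:** the geometric statistics come from Protocol 9.8.3, so record dropping them as a departure from it.

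The cost is one deleted sentence, short clarifications in three sections, one section 17 entry and a small change to derivation code. Adding the second extreme also means extra rows in Tables 2.2.13 to 2.2.16 and an adjustment to the Emax box plots. No new data are needed.

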12.4.3 Serum Pharmacodynamic Parameters

Pharmacodynamic parameters will be computed from the individual original and baseline-adjusted concentrations of serum calcium (uncorrected and corrected for serum albumin

levels), phosphate and calcium-phosphate product using a non-compartmental approach and actual sampling times. Pharmacodynamic parameters will be estimated for each dose.

The following parameters will be calculated using WinNonlin Phoenix version 6.3 or higher (Pharsight Corporation, Mountain View, California, USA):

- AUC_{last} : the area under the concentration versus time curve, from time of dosing to last measurable concentration
- TE_{max} : time to maximum effect
- E_{max} : maximum effect

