12.2 Handling BLQ, Zero Values, Missing Values

The following procedures will be used for original plasma PTH concentrations and serum PD data below the lower limit of quantification (LLOQ) and baseline-adjusted PTH and PD concentration data:

- Samples that are BLQ are reported as <LLOQ on the data listings, where LLOQ is replaced by the actual value for LLOQ for specific PK or PD assay.
- Samples that are BLQ are treated as zero in the calculation of summary statistics (e.g. mean, SD, etc.) for the plasma concentrations at individual time points.
- Mean concentrations are reported as zero if all values are BLQ or zero, and no other descriptive statistics are reported. If the calculated mean (\pm SD) concentration is less than the LLOQ, the value will be reported as calculated. The mean values derived using these conventions will be used to create the mean plasma concentration versus time plots.
- For calculation of area under the plasma concentration curve (AUC), BLQ values are set equal to zero in the dataset loaded into WinNonlin for pharmacokinetic analysis. WinNonlin uses the zero values that occur before the first time point with a concentration greater than LLOQ. Values that are BQL after the first measurable concentration are set to “missing” in the dataset loaded into WinNonlin.
- Missing values will not be imputed.

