12.4.1 Original Pharmacodynamic Data

Blood samples for PD analysis will be collected at Predose 2 (within 30 min prior to dose administration), 4, 8, 12 and 24 hours after dose administration of rhPTH(1-84) for the determination of concentrations of serum calcium (uncorrected [total] and corrected for serum albumin levels), phosphate. Serum calcium will be corrected for serum albumin levels using the following equation:

Corrected calcium (mmol/L) = serum calcium (mmol/L) + 0.02 (40 - serum albumin (g/L))
(Parent X, 2009)

The serum calcium-phosphate product (using albumin-corrected calcium) will also be determined. This is calculated as serum calcium concentration (albumin-corrected) x serum phosphate concentration.

Individual original concentrations of serum total calcium, albumin-corrected calcium, phosphate and calcium-phosphate product will be listed and summarized with descriptive statistics (number, arithmetic mean, SD, CV%, median, minimum, maximum) by ethnic group, dose and time point.

Figures of individual original concentration-time profiles and mean (\pm SD) will be generated on linear scale for serum total calcium, albumin-corrected calcium, phosphate and calcium-phosphate product by ethnic group and dose. The mean plots will be created for the original concentrations of the above four PD markers by overlaying the mean values for each ethnic group and dose on the same figure.

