12.4.4 Statistical Analysis of Pharmacodynamic Parameters

Pharmacodynamic parameters of serum total calcium, albumin-corrected calcium and phosphate and calcium-phosphate product will be listed and summarized with descriptive statistics (number, arithmetic mean, SD, CV%, median, minimum, maximum, geometric mean, and geometric CV%) by ethnic group, dose and time point. This will be done for both original and baseline-adjusted values.

Box-Whisker plots for AUC_{last} and E_{max} based on both original and baseline-adjusted concentrations will be prepared for the 100 μ g dose with the Japanese cohort and Non-Japanese cohort side by side.

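### Baseline-adjusted PD AUClast has no fixed end point: on the natural reading, a 24 h value at or below baseline drops the 12–24 h area for that subject

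*SAP*

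**What the plan says.** SAP 12.4.2 defines the adjusted data: "Baseline-adjusted concentrations of PD markers are to be calculated by subtracting the appropriate baseline values from the original concentrations at each time point". It then adds a floor: "If the baseline-adjusted concentration gives a negative value then the baseline-adjusted concentration should be set to zero".

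SAP 12.4.3 computes AUClast from both the original and the adjusted values and defines it as "the area under the concentration versus time curve, from time of dosing to last measurable concentration". No fixed 0–24 h PD area is defined, and no trapezoid rule is given for PD. The linear-up/log-down rule in SAP 12.3.3 is stated for PTH only.

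SAP 12.2 says its rules cover "baseline-adjusted PTH and PD concentration data". For AUC it says: "Values that are BQL after the first measurable concentration are set to" missing.

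PD samples are taken predose and at 4, 8, 12 and 24 h (SAP 12.4.1), so nothing lies between 12 and 24 h. Protocol 2.1 describes the calcium response to rhPTH(1-84) as dose-related, "with maximum mean increases (approximately 0.125 to 0.175 mmol/L) observed 12 hours after dosing", and adds that levels had not come back to baseline at 24 h.

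Under SAP 12.4.4, AUClast is summarised by ethnic group and dose. Box plots of AUClast and Emax "based on both original and baseline-adjusted concentrations will be prepared for the" 100 µg dose, with the two cohorts side by side.

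**The concern.** AUClast suits a drug concentration that falls below an assay limit. Here it is applied to a change from baseline in an endogenous marker. The end of integration then depends on the sign of one difference between two single samples.

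A subject 0.01 mmol/L above baseline at 24 h is integrated over 24 hours. A subject at baseline is integrated over 12, and the dropped segment starts at about the time of the maximum mean calcium rise. Two nearly identical responses can therefore give very different areas.

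The parameter serves two secondary objectives: the PD comparison at 100 µg with 12 subjects per group, and the description of PD at 25 and 50 µg. Because the calcium rise is dose-related, subjects may be back at baseline by 24 h more often at the lower doses. The window would then vary with dose.

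**Working it through.** The plan states no PD AUC figure, so there is nothing to reproduce.

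**Inputs from the documents.** Grid 0, 4, 8, 12, 24 h (SAP 12.4.1); peak mean calcium rise p = 0.125–0.175 mmol/L at 12 h (Protocol 2.1); floor at zero (SAP 12.4.2).

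**Assumed.** Response shape, residual rise at 24 h, between-subject and per-sample variability.

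**1. One subject, linear rise to 12 h, 24 h value zero (linear trapezoid).**
- 0–12 h: 2(0 + p/3) + 2(p/3 + 2p/3) + 2(2p/3 + p) = 6p.
- 12–24 h: 6(p + 0) = 6p.
- Area to 12 h only: 6p = 0.75 to 1.05 mmol·h/L. Area to 24 h with the zero kept: 12p = 1.50 to 2.10. Loss 50%.

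**2. Other shapes.** Let the rises at 4, 8 and 12 h be a, b and c as fractions of the peak. The area to 12 h is p(4a + 4b + 2c) and the lost segment is 6cp.

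| Shape | a + b | c | Loss |
|---|---|---|---|
| Convex | 0.60 | 1 | 6/10.4 = 57.7% |
| Linear | 1.00 | 1 | 6/12 = 50.0% |
| Concave | 1.45 | 1 | 6/13.8 = 43.5% |
| Plateau | 1.90 | 1 | 6/15.6 = 38.5% |
| Peak at 8 h | 1.60 | 0.7 | 4.2/12 = 35.0% |

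**3. Effect of the trapezoid rule.** Take p = 0.15, a linear rise and a 24 h value of +0.01.
- Linear: 0.90 + 6(0.15 + 0.01) = 1.86. Falling to 0.90 is a 52% cut.
- Log-down: 0.90 + 12(0.15 − 0.01)/ln(15) = 0.90 + 0.62 = 1.52. Falling to 0.90 is a 41% cut.
- Over all the shapes and peaks, log-down gives cuts of 28–50% from +0.01 and about 18–36% from +0.001.

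**4. How often.** Assume a mean residual rise m at 24 h, 30% between-subject variability in response, and per-sample SD σ at both baseline and 24 h. Then P(24 h change ≤ 0) = Φ(−m/√[(0.3m)² + 2σ²]). For m = 0.03, σ = 0.03: √(0.000081 + 0.0018) = 0.0434, and Φ(−0.69) = 24%.

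| m (mmol/L) | σ = 0.03 | σ = 0.05 |
|---|---|---|
| 0.10 | 2.7% | 9.6% |
| 0.06 | 9.6% | 20.5% |
| 0.03 | 24.5% | 33.7% |
| 0 | 50% | 50% |

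The formula takes the response as normal. With a lognormal response of the same CV the lowest entry is 2.3%, so the range for m = 0.03–0.10 is about 2–34%.

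**5. Effect on the group mean.** Simulation of 200,000 subjects, mean rises 0.05, 0.10 and 0.15 at 4, 8 and 12 h, same variability, baseline error shared across time points. The true mean area is 6(0.15) + 6(0.15 + m) = 1.8 + 6m. Differences from it are given for σ = 0.03 / 0.05:

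| m | AUClast, clipped | 0–24 h, clipped | 0–24 h, signed |
|---|---|---|---|
| 0.10 | +0.3% / +1.9% | +0.7% / +3.6% | about 0 |
| 0.06 | −1.1% / +0.2% | +1.2% / +5.5% | about 0 |
| 0.03 | −5.7% / −3.1% | +2.7% / +8.2% | about 0 |
| 0 | −15.7% / −7.8% | +6.4% / +13.0% | about 0 |

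Truncation lowers the mean and the zero floor raises it, so they partly cancel in AUClast. Fixing the window while keeping the floor leaves the upward error. Only the signed area is unbiased throughout.

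**The case against.** **The truncation is not written down.** The set-to-missing sentence in SAP 12.2 names values below the assay limit. A baseline-adjusted zero is derived from a calcium value that was quantified, and the same section mentions BLQ and zero as separate things. If a zero counts as measurable, nothing is truncated. This stands as a point about wording. But 12.2 has zero values in its title and baseline-adjusted PD data in its scope, and a floor value of zero is not naturally a measurable concentration. Two readings that can differ twofold for a subject need settling.

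**Calcium had not returned to baseline at 24 h.** Protocol 2.1 says so. The statement is about levels overall and is introduced with reference to hypoparathyroidism, so it does not rule out individual healthy subjects at or below baseline. It does mean that the case of a mean fully back at baseline should not be taken as the expected one at 100 µg.

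**Stronger readings are tempting.** A reader might infer that the parameter is typically halved, or that group means are clearly biased downward and spread is inflated. The documents do not support this. Halving applies only to an affected subject, with a particular shape and a linear rule. Against a fixed window that keeps the zero floor, AUClast looks 8–10% low at m = 0.03, but that comparator is itself too high. Against the true area the shortfall is 3–6%. Spread depends on the comparator too: at m = 0.03 the CV of AUClast is 55% (σ = 0.03) and 69% (σ = 0.05), against 48% and 69% for the signed 0–24 h area.

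**The analysis is descriptive.** There is no PD test, and Emax, original-scale AUClast, per-time-point summaries and profile plots are also reported. This stands and limits the consequence.

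**Conclusion.** The window defect holds on the natural reading of SAP 12.2, 12.4.2 and 12.4.3 together; on the other reading the SAP is unclear and should say so. An affected subject loses about 35–58% of the area with a linear trapezoid, and less with log-down.

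Across a group the effect is modest under the assumptions used: about 2–34% of subjects truncated, and a mean within −6% to +2% of the true area, for a residual mean rise of 0.03–0.10 mmol/L and a per-sample SD of 0.03–0.05. If the mean is back at baseline by 24 h, which is more plausible at 25 and 50 µg than at 100 µg, half the subjects are truncated and the mean is 8–16% low. That last figure keeps the assumed 0.15 mmol/L peak and is only a guide for lower doses. The documents give neither individual 24 h values nor a per-sample SD, so frequency rests wholly on these assumptions.

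A reader might also infer a bias between the ethnic groups. The same rule applies to both, and nothing in the documents shows that their return to baseline differs. The point concerns one descriptive, secondary parameter. The primary PK comparison, original-scale PD AUC and Emax are unaffected. It should be corrected because a better definition is available at almost no cost.

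**What to change.** - In SAP 12.4.3, replace AUClast for baseline-adjusted PD markers with AUC0-24, by linear trapezoid over predose (set to 0), 4, 8, 12 and 24 h.
- Compute it from signed changes from baseline, keeping zeros and negative values. The floor in 12.4.2 must not apply to this parameter; a fixed window on floored values would still read too high.
- State that the set-to-missing rule in SAP 12.2 does not apply to baseline-adjusted PD data.
- Use AUC0-24 in the SAP 12.4.4 tables and the 100 µg box plots.

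The cost is SAP wording and a partial-area setting in the software already planned, with no new samples. The downside is that signed areas can be negative, so the geometric mean and geometric CV must be dropped for this parameter; arithmetic mean, SD, median and range remain.
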